8.4. Subgroup Analyses of Efficacy Variables

Subgroup analyses of efficacy variables are specified in [Section 8.1.1](#).

9. Safety and Tolerability Analysis

Safety will be assessed by evaluating adverse events (AEs), vital sign measurements, use of oxygen therapies, changes in levels of biomarkers, clinical laboratory test results, electrocardiograms (ECGs), physical examination findings, and concomitant medications and

therapies.

All safety analyses will be performed on the Safety Population. Separate outputs will be produced for Part 1 and Part 2 of the study.

9.1. Adverse Events

All AEs, TEAEs, and SAEs will be coded using the Medical Dictionary for Regulatory Activities (MedDRA) v24.0.

Treatment-emergent AEs are defined as AEs that first occur or worsen in severity after the first dose of IP and prior to the 30 days after last administration of IP.

An overall summary of number and percentage of participants with at least one TEAE, severe TEAE, treatment-related TEAE, AE leading to discontinuation, AE leading to death, at least one SAE, and treatment-related SAE will be presented.

The number and percent of participants reporting treatment emergent TEAEs, grouped by MedDRA SOC and preferred term (coded using MedDRA v24.0) will be tabulated for the overall safety population and by treatment group. In the case of multiple occurrences of the same TEAE within the same subject, each subject will only be counted once for each preferred term.

Causality, and severity of TEAEs (by CTCAE v5.0 grade) will be tabulated. In the summaries showing severity and relationship to study medication the event with the maximum severity or strongest relationship will be reported. Although not anticipated, if a particular event is missing the severity and/or relationship, missing severities will be imputed as CTCAE Grade 3 and missing relationships will be imputed as related. CTCAE Grade 3 (i.e., Severe or medically significant but not immediately life-threatening) is chosen since higher grades (i.e., Grade 4 [life-threatening] or Grade 5 [death]) are most unlikely to be unobserved and Grade 3 is considered sufficiently deleterious when the severity is in question. Related is chosen for missing relationships as it is the most conservative option. Missing data for severities and relationships will be reported with counts and percentages prior to this imputation.

An additional analysis will be done for Part 2 participants for AEs with a greater severity than mild and AEs related to study treatment. The frequency and percentage of participants experiencing each type of event by Day 60 will be presented in each treatment arm. The difference in proportions, 95% CI derived, p-value comparing varespladib and placebo from a 2-proportion Z-test will also be presented.

In the AE data listings, all AEs will be displayed. AEs that are not treatment-emergent will be flagged.

9.1.1. Adverse Events Leading to Withdrawal of the Study Drug

A summary of incidence rates (frequencies and percentages) of TEAEs leading to withdrawal of study drug by system organ class, and preferred term will be prepared for the safety population overall and treatment.

AD-ST-33.06 Effective date: 12-Nov-2020

A data listing of TEAEs leading to withdrawal of study drug will also be provided, displaying details of the event(s) captured on the CRF.

9.1.2. Deaths and Serious Adverse Events

Any deaths that occur during the study will be listed.

SAEs will be listed and also tabulated by system organ class and preferred term and presented by treatment.

9.2. Clinical Laboratory Evaluations

Laboratory test results for chemistry, coagulation, hematology and urinalysis will be summarized descriptively by treatment and visit as both observed values and change from baseline values.

The number and percentage of participants with at least 1 post-baseline potentially clinically significant abnormality will be presented by treatment group for selected parameters. The number of participants with clinical laboratory values below, within, or above the normal range by visit and in relation to baseline will be tabulated for each clinical laboratory analyte by treatment group (shift table).

Individual data listings of laboratory results will be presented for each subject. Flags will be displayed for values outside of the laboratory's normal reference limits.

9.3. Biomarkers

Observed values and changes from baseline in biomarkers such as cardiac troponin level, CRP, and ferritin will be summarized using descriptive statistics by visit. The safety biomarkers data will be provided in a listing.

9.4. Vital Signs and Pulse Oximetry

Descriptive summaries of actual values and changes from baseline will be calculated systolic blood pressure, diastolic blood pressure, heart rate, respiratory rate, body temperature, and SpO₂.

The number and percentage of participants with at least 1 post-baseline potentially clinically significant abnormality will be presented by treatment group for selected parameters.

Individual data listings of vital signs (observed and change from baseline) will be presented for each subject.

9.5. 12-Lead Electrocardiogram

Descriptive summaries of observed values and changes from baseline will be calculated for heart rate, PR interval, QRS interval, QT interval and QTcF by visit and treatment group.

Frequencies and percentages of investigator interpretation of ECG results (normal, abnormal clinically significant, and abnormal not clinically significant) will be presented by visit and treatment group.

The safety ECG data will be provided in a listing.

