### 8.2. Study Entry Criteria

#### 8.2.1 Inclusion Criteria

A participant will be eligible for study participation if he or she meets all of the following criteria:

1. Participant is hospitalized with severe COVID-19 illness, defined in accordance with the FDA Guidance for Industry – COVID-19: Developing Drugs and Biological Products for Treatment or Prevention (May 2020):
  - a. Severe illness:
    - i. Symptoms suggestive of severe systemic illness with COVID-19, which could include any symptom of moderate illness or shortness of breath at rest, or respiratory distress
    - ii. Clinical signs indicative of severe systemic illness with COVID-19, such as respiratory rate  $\geq 30$  per minute, heart rate  $\geq 125$  per minute,  $\text{SpO}_2 \leq 93\%$  on room air at sea level or partial pressure of oxygen  $\text{PaO}_2/\text{fraction of inspired oxygen FiO}_2 < 300$
  2. Participant has a positive virologic nucleic acid amplification test (NAAT) indicating SARS-CoV-2 infection in a sample collected  $< 72$  hours prior to randomization.
  3. Participant is between the ages of 18 and 80 years at the time of enrollment.
  4. Participant (or legally authorized representative) provides informed consent prior to initiation of any study procedures.
  5. Participant agrees to not participate in another clinical trial for the treatment of COVID-19 or SARS-CoV-2 through Day 28.
  6. Participant has adequate hematologic status (in the absence of transfusion and growth factor support for at least 28 days), defined as follows:
    - a. Absolute neutrophil count (ANC)  $\geq 1.5 \times 10^9/\text{L}$
    - b. Platelet count  $\geq 75 \times 10^9/\text{L}$
    - c. Hemoglobin  $\geq 9 \text{ g/dL}$
  7. Participant has an Eastern Cooperative Oncology Group (ECOG) performance score of 0-2.

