#### 8.2.2 Exclusion Criteria

A participant will be excluded from the study if he or she meets any of the following criteria:

1. Participant has mild, moderate, or critical COVID-19 defined in accordance with the FDA Guidance for Industry:

- a. Mild COVID-19:
  - i. Symptoms of mild illness with COVID-19 that could include fever, cough, sore throat, malaise, headache, muscle pain, gastrointestinal symptoms, without shortness of breath or dyspnea
  - ii. No clinical signs indicative of moderate, severe, or critical severity
- b. Moderate COVID-19:
  - i. Symptoms of moderate illness with COVID-19, which could include any symptom of mild illness (fever, cough, sore throat, malaise, headache, muscle pain, gastrointestinal symptoms) or shortness of breath with exertion
  - ii. Clinical signs suggestive of moderate illness with COVID-19, such as respiratory rate  $\geq 20$  breaths per minute, peripheral oxygen saturation ( $\text{SpO}_2$ )  $> 93\%$  on room air at sea level, heart rate  $\geq 90$  beats per minute
  - iii. No clinical signs indicative of severe or critical illness
- c. Critical COVID-19:
  - i. Respiratory failure defined based on resource utilization requiring at least one of the following:
    - Endotracheal intubation and mechanical ventilation
    - Oxygen delivered by high-flow nasal cannula ([HFNC] heated, humidified, oxygen delivered via reinforced nasal cannula at flow rates  $> 20$  L/min with fraction of delivered oxygen  $\geq 0.5$ )
    - Noninvasive positive pressure ventilation
    - ECMO, or
    - Clinical diagnosis of respiratory failure (i.e., clinical need for one of the preceding therapies, but preceding therapies not able to be administered in setting of resource limitation)
  - ii. Shock (defined by systolic blood pressure  $< 90$  mmHg, or diastolic blood pressure  $< 60$  mmHg or requiring vasopressors)
  - iii. Multi-organ dysfunction/failure

2. Participant has taken investigational medications within 7 days or 5 half-lives prior to enrollment, whichever is shorter.
3. Participant has required any new form of sedation, anxiolysis or central nervous system (CNS) depressant within the 48 hours prior to enrollment that would interfere with neurologic assessments at enrollment.
4. Has history of cerebrovascular accident or intracranial bleeding of any kind, acute coronary syndrome, myocardial infarction, or severe pulmonary hypertension.

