### **13.1.5.2 Clinical Laboratory Evaluations, Vital Signs, Electrocardiograms, and Pulse Oximetry**

Summary statistics of clinical laboratory measures will be presented by treatment group for each assessment. The number and percentage of participants with at least 1 post-baseline potentially clinically significant abnormality will be presented by treatment group for selected parameters.

The same approach will be used for vital signs, ECGs, and pulse oximetry.

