6.1. Statistical Definitions and Algorithms

6.1.1. Baseline

The last observation recorded before the first administration of IP will be used as the baseline observation for all calculations of change from baseline.

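### SAP 9.4 counts vital-sign and SpO2 abnormalities without a new-or-worse condition, so for the signs that select patients into the trial the count can mix persisting entry illness with on-treatment worsening

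*SAP*

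**What the plan says.** **The count.** SAP 9.4 states: "The number and percentage of participants with at least 1 post-baseline potentially clinically significant abnormality will be presented by treatment group for selected parameters". Protocol 13.1.5.2 sets out the same count for laboratory measures and then extends it: "The same approach will be used for vital signs, ECGs, and pulse oximetry". Neither document names the selected parameters or gives the limits.

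**What stands beside it.** SAP 9.4 also plans this: "Descriptive summaries of actual values and changes from baseline will be calculated systolic blood pressure, diastolic blood pressure, heart rate, respiratory rate, body temperature". The same summaries cover SpO2, and listings give observed values and changes for each subject. Baseline is defined in SAP 6.1.1: "The last observation recorded before the first administration of IP will be used as the baseline observation for all calculations of change from baseline". That sentence governs change scores. The abnormality count does not refer to it.

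**Related displays.** For laboratory values, SAP 9.2 adds a shift table of values "below, within, or above the normal range by visit and in relation to baseline". For adverse events, SAP 9.1 requires first occurrence or worsening after the first dose.

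**Who enters.** Inclusion criterion 1 (Protocol 8.2.1) asks for "Clinical signs indicative of severe systemic illness with COVID-19, such as respiratory rate" of at least 30 per minute, heart rate of at least 125, SpO2 of 93% or less on room air, or PaO2/FiO2 below 300. Moderate cases, described as having "No clinical signs indicative of severe or critical illness", are excluded (Protocol 8.2.2).

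**The concern.** Three of the four example entry signs (respiratory rate, heart rate, SpO2) are also in the SAP 9.4 parameter list. A participant whose entry tachypnoea, tachycardia or hypoxia simply lasts into the first days of treatment is counted exactly like one whose sign first appears, or gets worse, on study drug. Vital signs and SpO2 are recorded daily while the participant is in hospital (Schedule of Events), so a persisting sign has many chances to produce the single flag needed.

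What is at stake is how well one safety display can show harm. Adverse-event reporting may not fill the gap: under Protocol 11.1.1, worsening COVID-19 is not automatically an adverse event unless the investigator attributes it to study drug. The point also bears on the current report, because SAP section 10 leaves the Part 1 safety analysis unchanged. With Part 1 arms of 5, 5, 5 and 3, one persisting entry sign moves an arm's percentage by 1/5 = 20 points or 1/3 = 33 points.

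**Working it through.** The plan states no rate, limit or power for this count, so there is no figure to reproduce. Everything below is illustration under stated assumptions, except the arm sizes: 5, 5, 5 and 3 in Part 1, and 72/2 = 36 per arm planned in Part 2.

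**Step 1. What fills the count when the drug does nothing.** For one parameter let q be the share abnormal at baseline, s the chance of at least one abnormal reading afterwards given abnormal at baseline, and e the chance of a new abnormality given normal at baseline.

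- Flagged share = q·s + (1 − q)·e.
- Share of flags from patients already abnormal at entry = q·s / flagged share.

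Assume e = 0.10.

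| q | s | Flagged | Already abnormal at entry, among flagged |
|---|---|---|---|
| 0 | any | 0.10 | 0% |
| 0.3 | 0.7 | 0.21 + 0.07 = 0.28 | 75% |
| 0.5 | 0.9 | 0.45 + 0.05 = 0.50 | 90% |
| 0.9 | 1.0 | 0.90 + 0.01 = 0.91 | 99% |

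The row q = 0 describes a sign that is not abnormal at entry, such as low blood pressure. There the problem vanishes. Repeated readings raise s: with an assumed 30% chance per day and independent days, six days give 1 − 0.7^6 = 0.88.

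**Step 2. Dependence on the limit.** This is a simulation with no drug effect and one reading a day on Days 1 to 7.

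- SpO2 at entry: true value N(91, 2.5), reading SD 1.5, entry reading of 93 or less, rising 0.3 a day.
- Oxygen-titrated: true mean 94, SD 1.5, same reading SD, rising 0.1 a day, baseline taken in the same state.

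| SpO2 limit | Flagged, entry with low SpO2 | Of those, past the limit at baseline | Flagged, oxygen-titrated | Of those, past the limit at baseline |
|---|---|---|---|---|
| ≤93 | 97% | 100% | 64% | 44% |
| ≤92 | 91% | 88% | 42% | 33% |
| ≤90 | 64% | 66% | 9% | 16% |
| ≤88 | 30% | about 50% | 1% | 7% |

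For heart rate (true N(120, 10), reading SD 7, entry at 125 or more, falling 3 a day) the flagged shares are 87%, 70% and about 47% at limits of 120, 125 and 130. These shares are conditional on entering through that one sign. They are not whole-arm percentages.

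**Step 3. Lost contrast.** Suppose new or worsened abnormality truly occurs in 10% on placebo and 40% on varespladib, with 36 per arm, s = 0.9, and harm visible in the count as written only in patients normal at baseline. The expected shares are 0.9q + 0.10(1 − q) and 0.9q + 0.40(1 − q). Power (two-sided 0.05) is used only as a yardstick, since no test of this count is planned.

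| q | Count as written | Power | Baseline-normal patients only, power |
|---|---|---|---|
| 0 | 10% vs 40% | 0.85 | 0.85 |
| 0.3 | 34% vs 55% | 0.43 | 0.70 |
| 0.5 | 50% vs 65% | 0.25 | 0.55 |
| 0.7 | 66% vs 75% | 0.13 | 0.36 |
| 0.9 | 82% vs 85% | 0.05 | 0.14 |

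A count of new or worsened abnormality to which all 36 can contribute keeps the 30-point difference and 0.85 throughout. The last column shows why counting only new abnormalities is not enough: patients abnormal at entry must be able to contribute by getting worse.

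**Step 4. What a baseline condition removes.** In the low-SpO2 scenario, counting only values past a limit not met at baseline leaves 0.97 × 0 = 0%, 0.91 × 0.12 = 11%, 0.64 × 0.34 = 22% and 0.30 × 0.50 = 15%. Values past the limit with a fall of at least 3 points from baseline flag 6% to 9%. Counting either kind therefore gives at most 9%, 20%, 31% and 24%, against 97%, 91%, 64% and 30% as written.

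**The case against.** The strongest reply is that the size is unknown. The rule covers potentially clinically significant values for selected parameters. The limits could be stricter than the entry values or include a change from baseline, and respiratory rate, heart rate or SpO2 might not be selected. This stands, and it is why the parameters and limits must be stated.

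A reader might infer that every entrant is abnormal on these signs, so that the percentage sits near its ceiling in every arm and cannot show a drug signal. The documents do not support that. The entry list is open and includes PaO2/FiO2, so no single vital sign is required. The SpO2 criterion is on room air, while later readings follow institutional practice and may be on oxygen. Step 2 gives near-ceiling values only for limits close to the SpO2 entry value, and in the oxygen-titrated case most flags are new. Blood pressure and temperature are not on the list, and low blood pressure is excluded by the criterion beginning "Shock (defined by systolic blood pressure".

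It is also fair that baseline is handled elsewhere: change-from-baseline summaries, subject listings and, for SpO2, a change-from-baseline ANCOVA (SAP 8.2.6; SAP section 10 rules out hypothesis tests on Part 1 efficacy data). With 18 participants, listings can show individual worsening. This softens the point but does not remove it, because group means by visit do not separate persisting from worsening individuals. Finally, SpO2 is a secondary efficacy endpoint and is not listed as a safety endpoint in SAP 2.2.2, although Protocol 10.3.3 names pulse oximetry among the safety variables.

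**Conclusion.** The point holds as a dilution problem in one descriptive safety display. For respiratory rate, heart rate and SpO2, the count as written can combine persisting entry illness with on-treatment worsening. It would be wrong to read this as bias: with no drug effect, randomised arms fill alike.

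The amount cannot be derived from the documents. It is large if the limits lie near the entry values (97% flagged at an SpO2 limit of 93%, all already past it at baseline) and small if they are more extreme or readings are taken on oxygen (down to 1%). In the illustration, a 30-point difference shrinks to 21 points when 30% are abnormal at entry and to 9 points when 70% are. These figures rest on assumed limits, variability, recovery rates and harm. For blood pressure and temperature the argument does not apply. This is a worthwhile, low-cost improvement, and it does not undermine the safety analysis as a whole.

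**What to change.** In SAP 9.4, before unblinding:

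1. Name the selected parameters and state the limit for each.
2. Count a value past its limit only if the limit was not met at the SAP 6.1.1 baseline, or if the value is worse than that baseline by a minimum change stated in advance for each parameter.
3. Add a shift table from baseline to worst post-baseline value for vital signs and SpO2, by treatment group.
4. Keep the count of all abnormalities as a supporting listing.

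Protocol 13.1.5.2 can stay as it is, with the detail in the SAP. The cost is a short SAP edit and one extra table from data already collected. The downside is small: an entry abnormality that merely persists leaves the main table, though it stays visible in the shift table and the listing. The rule does not remove all background flags, since readings that vary around the limit will still produce some new ones.

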## 2.2. Schedule of Events

**Table 2-1: Schedule of Events**

Assessment	Screening/ enrollment	Treatment Period							Follow-up Period										
		1 a	2	3	4	5	6	7	8	9	10	11	12	13	14 [±2]	15, 16, 17, 18, 19, 20	21 [±2]	28 [±2] or ET	45 [±3]
Study Day	-1 a																		
Written informed consent	X																		
Inclusion/exclusion criteria review	X																		
Medication history	X																		
Demographics	X																		
Medical history	X																		
Vital signs (hospitalized patients) b	X	X	X	X	X	X	X	X	X	X	X	X	X	X	X	X	X	X	X
Vital signs (outpatients) b					X		X								X			X	
Peripheral oxygen saturation (SpO 2 ) (hospitalized patients) b	X	X	X	X	X	X	X	X	X	X	X	X	X	X	X	X	X	X	X
Peripheral oxygen saturation (SpO 2 ) (outpatients) b					X		X								X			X	
Height, weight c	X																	X	
12-lead electrocardiogram d	X		X		X		X								X			X	
Physical examination e	X	X		X		X		X										X	
Neurological assessment	X	X		X		X		X										X	
Nasopharyngeal swab f	X																		
Clinical laboratory tests																			
• CBC																			
• Blood chemistry																			
• Coagulation profile																			
• Biomarkers g																			
• sPLA2 activity																			
• Urinalysis																			

Assessment	Screening/ enrollment	Treatment Period							Follow-up Period											
		-1 a	1 a	2	3	4	5	6	7	8	9	10	11	12	13	14 [±2]	15, 16, 17, 18, 19, 20	21 [±2]	28 [±2] or ET	45 [±3]
Study Day																				
Serum pregnancy test	X																	X		
PK blood sample b		X	X	X																
WHO 9-point ordinal scale	X	X	X	X	X	X	X	X	X	X	X	X	X	X	X	X	X	X	X	X
Administer study intervention i		X	X	X	X	X	X	X	X											
Concomitant medications and therapies	X	X	X	X	X	X	X	X	X	X	X	X	X	X	X	X	X	X		
Adverse events	X	X	X	X	X	X	X	X	X	X	X	X	X	X	X	X	X	X	X	X

The Day 1, 4, 7, 14, and 28 visits will be performed **in person** (either at the hospital/site or via a home health provider).

The Day 2, 3, 5, 6, 8, 9, 10, 11, 12, 13, 15, 16, 17, 18, 19, 20, 21, 45, and 60 visits for discharged participants **may be conducted by phone or via ePRO**.

Note: Participants will be assessed daily per standard of care while hospitalized.

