Abbreviations: CBC = complete blood count; COVID-19 = coronavirus disease 2019; ePRO = electronic patient-reported outcome; ET = early termination; PK = pharmacokinetic; SAE = serious adverse event; sPLA2 = secretory phospholipase 2; SpO2 = peripheral oxygen saturation; WHO = World Health Organization

- a Screening, enrollment, and Day 1 of the Treatment Period can take place on the same day if the required screening test results are available.
- b Vital signs and SpO2 will be assessed per institutional practice and recorded daily through Day 28 while hospitalized. Vital signs collection is not required prior to collection of PK blood samples, and daily vital signs may be collected before or after PK blood samples as local procedures allow.
- c Weight at all marked visits; height at screening only.
- d Initial EKG screening should be performed within 24 hours of randomization
- e Complete physical examination at Screening; targeted physical examination at subsequent visits.
- f Nasopharyngeal swab for virologic testing, if not collected within the previous 72 hours. Nucleic acid amplification test (NAAT) confirmation of COVID-19 in a sample collected < 72 hours prior to randomization is required.
- g Biomarkers will include cardiac troponin, C-reactive protein, and ferritin.
- h Pharmacokinetic samples will be drawn from all participants in Part 1, and in a subset of approximately 14 participants in Part 2, at the following timepoints:
  - Part 1 all participants: Days 1 and 3: pre-first dose and 0.5, 1, 2, 3, 4, 6, 8, and 12 hours post-first dose. Day 2: pre-morning dose.
  - Part 2 PK participants: Day 3: pre-morning dose and 0.5, 1, 2, 3, 4, 6, 8, and 12 hours post-morning dose.
  - PK samples may be drawn via a home health provider for participants who are not hospitalized.
  - The 12-hour PK samples may be omitted for participants who are not hospitalized.
  - Samples should be drawn within windows for each timepoint: ± 15 minutes for 0.5 hour timepoint, ± 30 minutes for 1, 2, 3 and 4 hour timepoints, and ± 1 hour for 6, 8 and 12 hour timepoints.
- i There are 7 complete days of treatment. Depending on initial dose administration time, the final dose may conclude on calendar day 8.

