### 10.2. Study Periods and Visits

Participants will be assessed daily per standard of care while hospitalized and on a regular basis after discharge. The Day 1, 4, 7, 14, and 28 visits will be performed in person (either at the hospital/site or via a home health provider) to assess safety, obtain blood and urine samples for laboratory tests, and obtain clinical outcome data. The Day 2, 3, 5, 6, 8, 9, 10, 11, 12, 13, 15, 16, 17, 18, 19, 20, 21, 45, and 60 visits for discharged participants may be conducted by phone or via ePRO devices.

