### **10.2.3 Follow-up Period**

#### **10.2.3.1 Days 8, 9, 10, 11, 12, and 13**

- If hospitalized, measure vital signs and SpO2 per institutional practice
- Evaluate the participant using the WHO 9-point ordinal scale
- Record concomitant medications and concomitant therapies
- Assess and record AEs

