#### **10.3.3.2 Clinical Examinations**

##### **10.3.3.2.1 Vital Signs and Peripheral Oxygen Saturation (SpO2)**

Vital signs (including body temperature) and peripheral oxygen saturation (SpO2) will be assessed at the timepoints indicated in the Schedule of Events ([Table 2-1](#)) per institutional practice.

If the participant has multiple vital sign or SpO2 assessments on a given day, an assessment measured between 6 am-noon should be recorded in the eCRF, if possible, for consistency.

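### The ever-abnormal count for vital signs and SpO2 in SAP 9.4 depends partly on length of stay, because participants are measured daily in hospital but only on the in-person days after discharge

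*SAP*

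**What the plan says.** **Measurement.** Footnote b of Protocol Table 2-1 says vital signs and SpO2 "will be assessed per institutional practice and recorded daily through Day 28 while hospitalized". The table has a separate row, "Vital signs (outpatients"), and a matching SpO2 row, each with four post-baseline marks. I read these as Days 4, 7, 14 and 28, in line with Protocol 10.2: "The Day 1, 4, 7, 14, and 28 visits will be performed in person". The text for Days 8 to 13 reads "If hospitalized, measure vital signs", and Days 15 to 20 and Day 21 carry the same condition. If there are several readings in a day, Protocol 10.3.3.2.1 says that, if possible, "an assessment measured between 6 am-noon should be recorded in the eCRF". The number of readings is therefore roughly the number of days measured.

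**Analysis.** SAP 9.4 counts participants who were ever abnormal after baseline: "The number and percentage of participants with at least 1 post-baseline potentially clinically significant abnormality will be presented by treatment group for selected parameters". SAP 4.1 sets the default percentage denominator as all participants in the analysis population. SAP 9.4 promises descriptive summaries of values and changes but does not say by visit. The per-assessment layout comes from Protocol 13.1.5.2, which sets it out for laboratory data and adds: "The same approach will be used for vital signs, ECGs, and pulse oximetry".

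**Context.** Shorter hospitalization is a secondary objective (SAP 2.1.2). SAP section 10 leaves the Part 1 safety analysis unchanged after the recruitment pause.

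**The concern.** An ever-versus-never count rises with the number of times a participant is examined. Here that number follows the discharge date, which is itself an outcome. If one arm goes home sooner, it is examined less often and will tend to show fewer participants with an abnormality, even at the same risk per reading. If it stays longer, the bias runs the other way. Nothing in SAP 9.4 shows the number of readings or limits the comparison to days on which everyone is scheduled.

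A related problem affects any per-assessment summary. On Days 8 to 13 and 15 to 21 it would describe only those still in hospital, unless values are carried forward. On Days 7, 14 and 28 it would describe everyone. A change between adjacent days could then reflect who was measured.

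Vital signs are a named safety endpoint. Laboratory tests share the SAP wording but not the problem, since they fall on fixed in-person days. ECGs nearly escape it too, Day 2 being their only day that may be a phone visit after discharge.

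**Working it through.** The plan gives no figure to reproduce: no power calculation, no expected stay and no abnormality rate. Only the reading counts in step 1 come from the documents. The stays, risks and correlations are assumptions.

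**1. Readings per participant.** Count Days 2 to the last inpatient day, plus any later day among 4, 7, 14 and 28.

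| Last inpatient day | Post-baseline readings to Day 28 |
|---|---|
| 5 | 4 (Days 2–5) + 3 (Days 7, 14, 28) = 7 |
| 7 | 6 + 2 = 8 |
| 10 | 9 + 2 = 11 |
| 14 | 13 + 1 = 14 |
| 28 | 27 by footnote b; 21 by Table 2-1 columns |

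The two full-stay figures differ because Days 22 to 27 have no column in Table 2-1 and no procedure list, while footnote b asks for daily recording through Day 28.

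**2. Individual probability, independent readings.** With risk q per reading, P(at least one) = 1 − (1 − q)^n.

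| n | q = 2% | q = 5% |
|---|---|---|
| 4 (common days only) | 7.8% | 18.5% |
| 7 | 13.2% | 30.2% |
| 11 | 19.9% | 43.1% |
| 21 | 34.6% | 65.9% |
| 27 | 42.0% | 75.0% |

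**3. Arm averages.** Assume lognormal stays (log-SD 0.7, whole days, capped at Day 28), medians of 6 and 10 days, daily recording under footnote b, and the same q in both arms. Mean readings are 9.2 and 12.9. With independent readings:

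- q = 2%: 16.6% v 22.3%, a gap of 5.7 points.
- q = 5%: 36% v 46%, a gap of about 10 points.

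**4. Correlated readings.** Consecutive readings in one patient are unlikely to be independent. Let each participant's risk follow a Beta(a, b) distribution with a = q(1 − ρ)/ρ and b = (1 − q)(1 − ρ)/ρ, where ρ is the within-patient correlation. Then P(at least one) = 1 − B(a, b + n)/B(a, b), where B is the beta function. For q = 2% and ρ = 0.2, a = 0.08 and b = 3.92.

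| ρ | Gap at q = 2% | Gap at q = 5% |
|---|---|---|
| 0 | 5.7 points | about 10 points |
| 0.2 | 1.7 points (9.4% v 11.1%) | 3.6 points |
| 0.4 | 0.8 points | 1.8 points |

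**5. Effect on a by-day summary.** This is an illustrative simulation in which everything is assumed. True SpO2 starts at mean 91 (SD 1.5) and rises by a participant-specific daily amount (mean 0.5 control, 0.7 drug) to a ceiling of 97. Discharge occurs when it reaches 95, and measurement error has SD 1. Median stays are 11 and 8 days. The observed control mean is 93.2 on Day 13 (inpatients, 42% of the arm), 95.4 on Day 14 (everyone) and 93.2 on Day 15 (inpatients). The true arm difference on Day 13 is 95.85 − 95.26 = 0.59 points. Among inpatients it appears as 93.31 − 93.18 = 0.13. On Days 4, 7, 14 and 28 the observed and true means agree.

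**6. Common days only.** With n = 4 in both arms, equal risk per reading gives equal percentages whatever the stay.

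**The case against.** Several points on the other side stand.

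- **Size.** A reader might take 13% v 42% as the expected distortion. It compares two extreme individuals under independence, and the longer stay uses 27 readings where the schedule columns give 21 (34.6%). Arm averages differ far less, and a modest correlation removes most of the gap.
- **Part may be real.** A reader might infer that a shorter stay would produce fewer abnormalities with no true safety difference. The documents do not support that: participants who recover sooner plausibly have fewer abnormal values.
- **Trend.** A reader might say that SAP 9.4 builds in a jump between inpatient-only and common days. SAP 9.4 does not commit to by-visit tables. If they are produced, SAP 4.1 requires the number of non-missing values, so the fall in coverage would show. The general last-observation-carried-forward rule in SAP 6.1.4 might also apply, although the SAP does not tie it to safety data. Carrying values forward would add no new observation to an ever-abnormal count.
- **Consequence.** No test is planned for these counts; the two-proportion Z-test is for adverse events. Clinically relevant findings are also captured as adverse events through Day 60, and all readings are listed. In an arm of 5, 16.6% v 22.3% is 0.8 v 1.1 participants, while one participant is 20% of that arm, or 33% of an arm of 3.

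These points limit the weight of the finding. They do not remove the dependence of the count on length of stay.

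**Conclusion.** The concern holds in a limited form. The number of chances to be counted as abnormal follows length of stay, the denominator does not allow for it, and shortening stay is an aim of treatment. The reading counts (7 for discharge on Day 5, and 21 or 27 for a full stay) follow from the schedule. The size does not: under the assumed 6 v 10 day medians and equal 2% risk, the spurious gap runs from about 6 points with independent readings to about 2 at correlation 0.2 and under 1 at 0.4. The documents give neither stay distributions nor abnormality thresholds, so the range cannot be narrowed.

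In the Part 1 report chance will dominate. The point matters more for Part 2 (36 per arm planned, one participant recruited at the pause), for which section 10 foresees a SAP amendment. This is an inexpensive improvement to a descriptive safety display. It does not show that the safety conclusions would be wrong, and it does not justify replacing the all-readings table with common-day data, which would take most post-baseline dosing days out of the main display.

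**What to change.** In SAP 9.4:

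1. Keep the all-readings ever-abnormal table as the full safety display. Add, for each arm, the number of readings and the abnormal readings per participant-day measured. With equal risk per reading that rate does not depend on stay, although it still mixes inpatient with outpatient days.
2. Add a companion table of the same count limited to the in-person days scheduled for everyone (4, 7, 14 and 28), among participants alive and assessed.
3. Base any statement comparing arms or describing change over time on those days, and show the number assessed at each visit. State whether carry-forward applies to safety data.

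Separately, the visit text and schedule conflict and must be reconciled. Protocol 10.2.2.4 makes the Day 4 measurement conditional on being in hospital, although Day 4 is an in-person visit and Table 2-1 appears to mark it for outpatients. Protocol 10.2.2.5 sets no such condition for Day 5, which may be a phone visit. Part 1 has finished, so participants discharged before Day 4 may have no Day 4 reading, and the companion table should show this.

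The cost is SAP wording and one more table, with no new data. The common-day table omits dosing Days 2, 3, 5 and 6, which stay in the all-readings table and the listings.
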